4.2 Subgroups

ORR and PFS will be examined for the below subgroup analysis. When there is not a sufficient number of subjects in the subgroup, i.e., less than 10% of the whole population, the subgroup analysis will not be conducted:

- prior carfilzomib exposure (yes, no)
- number of prior lines of therapy (1, 2)
- timing of lenalidomide refractoriness (during maintenance: yes, no)
- **Cytogenetic risk measured by FISH (high risk (t(4;14), t(14;16), deletion 17p), standard risk)**
- **R-ISS (stage I, stage II, stage III)**
- **Prior anti-CD38 exposure (yes, no)**
- **Refractory to prior anti-CD38 treatment (yes, no)**
- **Prior bortezomib exposure (yes, no)**
- **Refractory to prior bortezomib treatment (yes, no)**

5. Definitions

Baseline

The baseline value is defined as the last assessment prior to the first dose of **any study treatment**. Absolute change from baseline will be defined as (post baseline value - baseline value). Relative change from baseline will be defined as (post baseline value - baseline value)/baseline value * 100%.

Complete Response Rate (CRR)

CRR is defined as the proportion of subjects whose best overall response is sCR or CR.

Cytogenetic Risk group as determined by Fluorescent in Situ Hybridization (FISH)

The FISH data will be used to determine the cytogenetic risk group as following:

High risk group: Subjects who have the cytogenetic abnormalities t(4;14) or t(14;16), and/or deletion 17p.

Standard risk group: Subjects who do not have any of the cytogenetic abnormalities t(4;14), t(14;16) and deletion 17p.

Missing: Subjects who cannot be identified as high risk nor standard risk.

Duration of Response (DOR)

DOR is defined as the time from first evidence of PR or better per IMWG-URC to the earliest of disease progression or death due to any cause for subjects with a best response of PR or better. DOR will be censored as per the PFS endpoint. Please see [Table 5-1](#)

$$\text{DOR} = [(\text{PD or death date whichever occurs first}) \text{ or date of censoring if censored} - \text{response start date} + 1] / 30.4.$$

End of Study

The end of study date is defined as the date when the last subject across all sites is assessed or receives an intervention **for evaluation in the study (ie, last subject last visit), including any additional parts in the study (eg, long-term follow-up, additional antibody testing), as applicable.** The study will end 4 years after the last subjects is enrolled in the study.

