It will be calculated as the planned cumulative dose of pomalidomide in mg divided by the planned number of weeks for the treatment per protocol based on the corresponding cycle and day of the last pomalidomide infusion. Per protocol, one cycle is 28 days (4 weeks), so the planned number of treatment weeks will be calculated as $4 \times (c-1) + j$, where c is the cycle in which the last pomalidomide dose is taken and $j=1$ if the last pomalidomide dose is taken on day 1 to 7 within the last cycle, $j=2$ if the last dose is given on day 8 to 14, $j=4$ if the last dose is given on day 15 to 21. The planned cumulative dose of pomalidomide is the summation of planned pomalidomide dose (mg) per week ($[7 \times 4, 7 \times 4, 7 \times 4, 0]$) across the planned treatment weeks.

Revised International Staging System (R-ISS) Stage at Baseline

R-ISS stage at baseline will be calculated using ISS, risk group by FISH, and LDH, based on the criteria published by the International Myeloma Working Group ([Palumbo, 2015](#)):

Stage I: ISS stage I and standard risk group by FISH and normal LDH

Stage II: Not R-ISS stage I or III

Stage III: ISS stage III and {either high-risk group by FISH or high LDH}

Sustained MRD[-]CR Rate

Sustained MRD[-]CR rate is defined as the proportion of subjects that maintain MRD[-]CR for 12 months +/- 4 weeks or more, ie, maintaining MRD[-]CR for at least 12 months minus 4 weeks is considered as sustained, after achieving MRD[-]CR status among the subjects who reach the MRD[-]CR status, disregarding when the first MRD[-]CR was reached.

Sustained MRD[-]CR Rate at 24 months

Sustained MRD[-]CR rate at 24 months is defined as the proportion of subjects that maintain MRD[-]CR for 12 months +/- 4 weeks or more, ie, maintaining MRD[-]CR for at least 12 months minus 4 weeks is considered as sustained, after achieving MRD[-]CR status in the time window of **Key Secondary** endpoint assessment.

Time to Response

Time from start of treatment to first date of confirmed PR or better.

Time to Response = (response start date – start of **any study** treatment date + 1) / 30.4

Time (month) since initial diagnosis

Time since initial diagnosis is defined as:

(Date of informed consent signed - date of first diagnosis of MM + 1) / 30.4

Treatment-emergent Adverse Event

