9.4 Demographic and Baseline Characteristics

The following demographic, baseline characteristics and baseline disease characteristics will be summarized for the Safety Analysis Set. These includes but not limited to the following,

- **Baseline demographic and Baseline characteristics**

- Age (years) (as continuous variable; as categorical variable: 18 to < 65, 65 to < 75, 75 to < 85, ≥ 85 years; **<65, ≥65; 18-<65, 65-<75, ≥75**)
- Sex (Male, Female)
- Ethnicity (Hispanic or Latino, Not Hispanic or Latino)
- Race (**If multiple races have been reported for a subject, the subject will be categorized as multiple race**)
- Region (**Europe, Non-Europe**)
- Weight (kg)
- Height (cm)
- Body mass index
- Body Surface Area (m²) (as continuous variable; as categorical variable: ≤ 2.2, > 2.2 m²)
- ECOG performance status (0, 1, 2)
- Hemoglobin (g/L) (as continuous variable; as categorical variable: < 105, ≥ 105 g/L)
- Absolute Neutrophil count (10⁹/L) (as continuous variable; as categorical variable: < 1.5, ≥ 1.5 * 10⁹/L)
- Platelet count (10⁹/L) (as continuous variable; as categorical variable: < 150, ≥ 150 * 10⁹/L)
- Corrected calcium (mg/dL) (as continuous variable; as categorical variable: ≤ 11.5, > 11.5 mg/dL)
- Creatinine clearance (CrCl, mL/min) (as continuous variable; as categorical variable: < 30, 30 - < 50, 50 - < 80, ≥ 80 mL/min)

Measured or calculated accordingly to the Cockcroft-Gault formula:

$$CrCl (mL/min) = \frac{(140 - Age(years)) \times Weight(kg)}{72 \times Serum Creatinine(mg/dL)} \times (0.85 \text{ female})$$

- Baseline LVEF (%)
- Hypertension history (yes, no)
- Cardiopulmonary history (yes **<by diagnosis category>**, no)

- **Baseline Disease characteristics**

- ISS stage at baseline (stage I, II, III)
- Revised ISS stage at baseline (stage I, II, III)

- **Prior lenalidomide treatment (yes, no)**
- **Refractory to prior lenalidomide treatment (yes, no)**
- **Prior PI treatment (yes, no)**
- **Prior anti-CD38 exposure (yes, no)**
- **Refractory to prior anti-CD38 treatment (yes, no)**
- **Prior bortezomib treatment (yes, no)**
- **Refractory to prior bortezomib treatment (yes, no)**
- Time (month) since initial diagnosis
- Type of measurable disease (both SPEP and UPEP, SPEP only, UPEP only, Free light chain and abnormal Kappa/Lambda ratio (SFLC) only)
- Plasma cell involvement in bone marrow (%)

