- MM subtype and immunoglobulin heavy chain and Light chain types (IgG, IgA, IgD, IgE, IgM, None; Kappa, Lambda, Not detectable within each subtype)
- Baseline beta2 microglobulin (mg/L) (as continuous variable; as categorical variable: < 3.5, 3.5 - < 5.5, ≥ 5.5 mg/L)
- Presence of plasmacytoma (yes, no)
- Prior Transplant (yes (Autologous, Allogeneic), no)
- **Prior tobacco use (yes, no)**
- Number of prior lines of therapy
- **Cytogenetic risk measured by FISH (high risk (t(4;14), t(14;16), deletion 17p), standard risk, missing)**
- Refractory to the last prior line of therapy
- **Albumin (g/dL) (as continuous variables; as categorical variable: <3.5, >=3.5)**
- Timing of refractoriness to Lenalidomide (during maintenance: yes vs no)
- **Time since last relapse (months)**

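### R-ISS stage II is a residual category with no missing level, so read literally it takes in subjects whose stage cannot be determined

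*SAP*

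**What the plan says.** SAP section 5 (Definitions, R-ISS stage at baseline) names three inputs: "R-ISS stage at baseline will be calculated using ISS, risk group by FISH, and LDH". A subject is stage I only if all three are favourable: ISS I, FISH standard risk, and LDH in the normal range. A subject is stage III if ISS is III and at least one of the two markers is adverse, that is, FISH high risk or LDH raised. Whoever is left over is the middle stage: "Stage II: Not R-ISS stage I or III".

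The same section gives the FISH risk group a third level: "Missing: Subjects who cannot be identified as high risk nor standard risk". The baseline list in section 9.4 carries that level through: "Cytogenetic risk measured by FISH (high risk (t(4;14), t(14;16), deletion 17p), standard risk, missing". For R-ISS, section 9.4 lists only "Revised ISS stage at baseline (stage I, II, III" and the ORR and PFS subgroups in section 4.2 list only "R-ISS (stage I, stage II, stage III".

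SAP section 8.3 deals with missing outcomes and incomplete dates, and Appendix A deals with dates only. Neither covers a missing staging component.

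**The concern.** Stage I needs three favourable values, all known. A subject with ISS I, normal LDH and no FISH result cannot meet it, cannot meet stage III, and so falls into stage II, although the true stage is I or II. A subject with ISS III, normal LDH and no FISH result also falls into stage II, although the true stage is II or III. Stage II can therefore collect possible stage I and possible stage III subjects, which blurs the contrast between stages.

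Two outputs are at stake. In the baseline table the FISH row would show missing subjects while the R-ISS row looked complete. In the subgroup analyses, ORR and PFS by stage would be computed on partly wrong groups. SAP section 2.1 does not carry over the protocol's exploratory comparison of PFS by risk group, so the section 4.2 subgroup is the only R-ISS analysis of PFS left in the SAP.

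**Working it through.** The documents give no figure for missing R-ISS or missing FISH, so there is no figure to reproduce. The check applies the three rules as written to every pattern of inputs.

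**Inputs (SAP section 5).** ISS: I, II, III or missing. FISH: standard, high or missing. LDH: normal, high or missing. That is 4 × 3 × 3 = 36 patterns. Complete patterns number 3 × 2 × 2 = 12 (1 is stage I, 8 are stage II, 3 are stage III). The remaining 36 − 12 = 24 have at least one missing component.

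**Method.** For each incomplete pattern, take the stage that the rule assigns, and compare it with every stage that could result once the missing values were known.

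| Incomplete pattern | Patterns | Stage as written | Possible true stage |
|---|---|---|---|
| ISS I, one marker known adverse, the other missing | 2 | II | II |
| ISS I, no marker known adverse | 3 | II | I or II |
| ISS II, FISH and/or LDH missing | 5 | II | II |
| ISS III, one marker known adverse, the other missing | 2 | III | III |
| ISS III, no marker known adverse | 3 | II | II or III |
| ISS missing, any FISH and LDH | 9 | II | two or three stages |

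**Result.** Stage II as written: 2 + 3 + 5 + 3 + 9 = 22. Stage III as written: 2. Stage I: 0. Undetermined but placed in stage II: 3 + 3 + 9 = 15. Correctly staged in spite of the gap: 2 + 5 + 2 = 9.

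**FISH alone missing.** There are 3 × 2 = 6 patterns. Two are undetermined (ISS I with normal LDH, ISS III with normal LDH), three are correctly stage II and one is correctly stage III.

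The table treats a missing ISS as wholly unknown. Under the section 5 ISS definition, a beta-2 microglobulin value without albumin can still exclude some ISS stages, so some real cases of incomplete ISS would be determined.

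**From patterns to subjects.** These are counts of patterns, not of patients. If FISH were missing in 10% to 20% of the 52 treated subjects (an assumption), that would be 5.2 to 10.4, or about 5 to 10 subjects with missing FISH. Only those with ISS I or III and no known high LDH, or with ISS also missing, are undetermined. That share is not given either.

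**Subgroup threshold.** Section 4.2 drops subgroups below 10% of the population: 0.10 × 52 = 5.2, so a stage needs at least 6 subjects. Moving a few subjects can decide whether stage I or stage III is analysed at all.

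**Primary and key secondary tests.** With 52 subjects the exact 90% interval excludes 60% at 38 or more responders, and excludes 3% at 5 or more subjects with MRD[-]CR. These cut-offs reproduce the powers in SAP Table 3-1 for 52 subjects (69.2%, 91.8%, 60.5%, 76.3%). R-ISS enters neither test.

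**The case against.** The SAP nowhere instructs that subjects with missing components go to stage II. Naming three inputs can be read as presupposing that all three are available, in which case the residual wording only divides subjects with complete data, and a program might return missing for the rest. This stands in part: the result follows from literal application, not from an explicit instruction. But the SAP expects missing FISH and gives no rule for what R-ISS then becomes, so two programmers could differ, and the one who follows the text gets stage II.

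The absence of a missing level in the lists is weak evidence. The FISH subgroup in section 4.2 also omits the missing level that section 5 defines, and the section 9.4 list is expressly open-ended. That is fair; the point rests on the residual definition, not on the lists.

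Missing inputs may be few. Protocol Table 2-1 requires a FISH sample before the first dose and schedules beta-2 microglobulin and chemistry at screening; albumin and LDH are in the chemistry panel (Table 12-1). Missing ISS or LDH should be uncommon. An uninformative FISH result remains possible: it is a local bone marrow test, and protocol section 9.2.2.2 assigns the first baseline aspirate sample to MRD sequence identification.

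A reader might infer that every subject with any missing component is misplaced. The table shows otherwise: ISS II subjects belong in stage II whatever is missing, as do ISS I subjects with one known adverse marker, and ISS III subjects with one known adverse marker are correctly stage III.

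**Conclusion.** The point holds in limited form. Because stage II is defined by exclusion and R-ISS has no missing level, the rule as written places subjects of undetermined stage in stage II: 15 of the 24 incomplete patterns. It is a minor defect, limited to the R-ISS baseline row and the R-ISS subgroups for ORR and PFS.

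Two larger inferences are not supported. The 5 to 10 subjects above are an assumed count of missing FISH, not of misclassified subjects; the number affected is unknown and, for missing FISH, smaller than that count. Nor does the gap affect how ORR is judged against the 60% reference: SAP section 9.5.1 compares only the lower confidence bound with the reference rate, and nothing in the plan adjusts that rate for R-ISS mix. The risk mix also stays visible through the separate baseline rows for ISS, FISH (with its missing level), beta-2 microglobulin and albumin.

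**What to change.** In SAP section 5, assign stage II only when the available ISS, FISH and LDH values rule out both stage I and stage III; assign stage III when its criteria are met on the known components; otherwise set R-ISS to missing. This moves the 15 undetermined patterns to missing and leaves the 9 determined ones where they are. A blanket rule that sets R-ISS to missing whenever any component is missing should be avoided, because it would discard those 9.

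Add the missing level to the R-ISS row in section 9.4, and state in section 4.2 that subjects with missing R-ISS are left out of the R-ISS subgroup analyses. The cost is one sentence in section 5 and two small matching edits. No new data are needed.

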6.1 Full Analysis Set

Not Applicable

6.1.1 Primary Analysis Set

Not Applicable

6.2 Safety Analysis Set

The Safety Analysis Set includes all enrolled subjects who received at least 1 dose of carfilzomib. The analysis of efficacy and safety analyses will be based on the Safety Analysis Set.

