6.4 Screen Failures

Screen failures are defined as subjects who consent to participate in the clinical study but are not subsequently enrolled in the study. A minimal set of screen failure information will be collected that includes demography, screen failure details (reasons for screen failure up to 3), eligibility criteria, and any serious adverse events.

Individuals who do not meet the criteria for participation in this study (screen failure) may be rescreened once. Refer to Section 9.1.1.

Subjects who experience a technical failure of local laboratory samples at screening (for example sample is lost or damaged in transit, or otherwise cannot be analyzed) will not be considered a screen failure. Lab samples may be retested during screening in such cases, subject to the screening window not being exceeded.

7. Treatments

Study treatment is defined as any investigational product(s) or non-investigational product(s) intended to be administered to a study subject according to the study protocol.

Note that in several countries, investigational product and non-investigational product are referred to as investigational medicinal product and non-investigational medicinal product, respectively.

The Investigational Product Instruction Manual (IPIM), a document external to this protocol, contains detailed information regarding the storage, preparation, destruction, and administration of each treatment.

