7.1.1.2.2 Dosage, Administration, and Schedule

Pomalidomide dose will be 4 mg per day orally on days 1 to 21 of each cycle until progression.

The planned dose (mg), dose administered (mg), start date, stop date, reason for dose change/withheld, reason for dose delay, are to be recorded on each subject's eCRF.

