7.1.2 Non-investigational Products

7.1.2.1 Dexamethasone: Dosage, Administration, and Schedule

Dexamethasone, a non-Amgen non-investigational product, will also be used in this study (Dexamethasone SmPC and USPI). Dexamethasone will be administered at least 30 minutes, but no more than 4 hours prior to carfilzomib on days of carfilzomib administration.

Dexamethasone will be administered at a dose of 40 mg on days 1, 8, 15, and 22 of each 28-day cycle up to progression during cycles 1 to 12.

Dexamethasone will be administered at a dose of 20 mg on days 1 and 15 of each 28-day cycle up to progression during cycles 13 onward.

For subjects \geq 75 years of age, the dose will be 20 mg during cycles 1 through 12 and 10 mg from cycles 13 onward.

The planned dose (mg), dose administered (mg), start date/time, stop date/time, route, reason for dose change/withheld, reason for dose delay, reason for dose interruption are to be recorded on each subject's eCRF.

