9.1.2 Treatment Period

Visits will occur per the Schedule of Activities (Table 2-1). Subjects assessed as eligible for the study will be enrolled and must start study treatment within 3 days of enrollment. On-study visits may be completed within 3 days. The date of the first dose of protocol-required therapies is defined as day 1. All subsequent doses and study visits will be scheduled based on the day 1 date. Administration of protocol-required therapies is to be administered last during each visit that it is required, unless otherwise indicated in the Schedule of Activities.

After discontinuation from study treatment, subjects who do not have confirmed PD are required to continue disease response assessments and report new antimyeloma treatment and will be followed every 28 ± 7 days until first subsequent antimyeloma

treatment, death, loss to follow-up, withdrawal of full consent, confirmed PD, or end of study, whichever comes first.

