3.2 Sample Size

The sample size was determined based on **feasibility** and the intent to optimize the power for testing the primary hypothesis at 1-sided alpha of 0.05. With 85 subjects (safety population), the power for testing the primary hypothesis and secondary hypothesis at 1-sided alpha of 0.05 was expected to be more than 85%. **In late 2021, enrollment was discontinued after 54 subjects were enrolled due to practical consideration.** As these estimates are based on **recent data available for the study population (eg, sub-populations within clinical trials CANDOR and A.R.R.O.W.),** additional scenarios, **including those based on the actual number of subjects who received at least one dose of carfilzomib (52 subjects),** for the experimental arm and power are included in [Table 3-1](#).

Table 3-1. Power for Hypothesized Treatment Effect

Hypothesis	Sample Size	H0	H1	Power
Primary	85	ORR \leq 60%	ORR \geq 75%	90.4%
	85	ORR \leq 60%	ORR \geq 80%	99.3%
	52	ORR \leq 60%	ORR \geq 75%	69.2%
	52	ORR \leq 60%	ORR \geq 80%	91.8%
Secondary	85	MRD[-]CR rate at 12 months \leq 3%	MRD[-]CR rate at 12 months \geq 10%	86.4%

	85	MRD[-]CR rate at 12 months \leq 3%	MRD[-]CR rate at 12 months \geq 12%	95.1%
	52	MRD[-]CR rate at 12 months \leq 3%	MRD[-]CR rate at 12 months \geq 10%	60.5%
	52	MRD[-]CR rate at 12 months \leq 3%	MRD[-]CR rate at 12 months \geq 12%	76.3%

ORR = overall response rate; MRD[-]CR = minimal residual disease negative complete response

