
Number of doses of pomalidomide administered

It is defined as the total number of non-zero doses of pomalidomide a subject received during the treatment period of the study

Number of doses of dexamethasone administered

It is defined as the total number of non-zero doses of dexamethasone a subject received during the treatment period of the study

Overall Response (OR)

OR is the best overall confirmed response of partial response (PR), very good partial response (VGPR), complete response (CR), or stringent complete response (sCR).

Overall Response Rate (ORR)

Overall Response Rate (ORR) is defined as the proportion of subjects that reach the overall response among all subjects who received at least 1 dose of the carfilzomib.

Overall Survival (OS)

OS is defined as time from start of treatment until death from any cause.

$OS = (\text{Death date or date of censoring if censored} - \text{start of any study treatment date} + 1) / 30.4$

Subjects still alive will be censored at the date last known to be alive. If the date last known to be alive is after the date that triggers the analysis (ie, the data cutoff date), the subject will be censored at the analysis trigger date.

Progression Free Survival (PFS)

PFS is defined as the time from the first dose date of any study treatment until the first documentation of disease progression or death due to any cause, whichever occurs first in the absence of subsequent anticancer therapy and if not > 70 days from the last non-NE, post-baseline disease assessment. PFS will be censored at the last non-NE, post-baseline disease assessment or the earlier of the following, where applicable: (a) the last non-NE, post-baseline disease assessment prior to subsequent anticancer therapy, or (b) the last non-NE, post-baseline assessment followed > 70 days later by disease progression or death; otherwise, at first dose date. Disease progression is based on the IMWG-URC [2016].

PFS time in months= [(PD or death date, whichever occurs first) or date of censoring if censored– start of treatment date + 1] / 30.4.

Table 5-1. Conventions for Censoring for PFS

Situation	Date of Progression or Censoring	Outcome
No PD or death, no new anticancer treatment	Last visit; otherwise, first dose date of any study treatment	Censored
No PD or death, new anticancer treatment	Last visit prior to new treatment; otherwise, first dose date of any study treatment	Censored

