9.1 General Considerations

The analyses of efficacy and safety will be based on the safety analysis set. In principle, continuous variables will be summarized by the non-missing sample size (n), mean, standard deviation, median, minimum, and maximum.

Categorical variables will be summarized by the n and percentage in each category.

Time to event endpoints will be summarized with Kaplan-Meier (KM) curves, KM proportions at select time points, KM quartiles (when estimable), the number of subjects with events, the number of subjects censored, and censoring reasons.

Duration of follow-up for time to event endpoints will be estimated using the reverse Kaplan Meier method (Schemper and Smith, 1996). Point estimates for efficacy endpoints will be accompanied by 2-sided 90% and 95% CIs including estimates of KM quartiles (Klein and Moeschberger, 1997), KM proportions (Kalbfleisch and Prentice, 1980), and binomial proportions (Clopper and Pearson, 1934).

The evaluation of whether the key secondary objective was met will follow a fixed-sequence approach using the 90% exact confidence interval: the key secondary objective is met only after the primary objective is met.

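### The only population for the safety tables requires a carfilzomib dose, while the adverse-event window opens at the first dose of any of the three drugs, so a subject dosed but never infused is tabulated nowhere

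*SAP*

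**What the plan says.** The Safety Analysis Set is defined identically in Protocol 10.2.1 and SAP 6.2: "The Safety Analysis Set includes all enrolled subjects who received at least 1 dose of carfilzomib". SAP 9.1 gives it full scope: "The analyses of efficacy and safety will be based on the safety analysis set". The ORR definition in SAP section 5 repeats the carfilzomib condition ("proportion of subjects that reach the overall response among all subjects who received at least 1 dose of the carfilzomib"), and the MRD[-]CR rate at 12 months has the same denominator.

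Treatment itself is defined more widely:

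- The opening of Protocol section 7 states: "Study treatment is defined as any investigational product(s) or non-investigational product(s) intended to be administered to a study subject according to the study protocol". Carfilzomib and pomalidomide are investigational products and dexamethasone is non-investigational, so all three count.
- Protocol 7.1.2.1: "Dexamethasone will be administered at least 30 minutes, but no more than 4 hours prior to carfilzomib on days of carfilzomib administration".
- Protocol 7.1.1.2.2: "Pomalidomide dose will be 4 mg per day orally on days 1 to 21 of each cycle until progression".
- Protocol 9.1.2: "The date of the first dose of protocol-required therapies is defined as day 1".
- SAP section 5 starts baseline, PFS, OS and the treatment-emergent window at the first dose of any study treatment.

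The documents report 54 subjects enrolled and 52 who received carfilzomib (Protocol synopsis and 10.1; SAP 3.2).

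**The concern.** The event window and the population that reports the events have different triggers. A subject who takes dexamethasone or pomalidomide on day 1, and then has an event, refuses or withdraws before any infusion, has treatment-emergent adverse events under the SAP's definition. That subject is outside the set on which the adverse-event tables are built. Describing the safety and tolerability of the combination is a stated secondary objective, and two of its three drugs can be given without the recipient being counted.

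The same subject is missing from the ORR denominator. In a single-arm, open-label trial judged against a fixed 60%, leaving out subjects after treatment has begun can affect the estimate.

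**Working it through.** **1. Does any other set or line pick the subject up?**

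| Place | Condition | Dosed but never infused |
|---|---|---|
| SAP 6.1 Full Analysis Set | not applicable | no |
| SAP 6.2 Safety Analysis Set | at least 1 carfilzomib dose | no |
| SAP 6.3 MRD Evaluable set | also requires carfilzomib | no |
| SAP 6.4 Modified Safety set | subset of 6.2 | no |
| SAP 6.5 Per Protocol set | subset of 6.2 | no |
| SAP Table 9-1 sensitivity analyses | other assessors, or subsets of 6.2 | no |
| SAP 9.2 disposition | either enrolled but not dosed, or treated (equated with the Safety population) | fits neither |

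**2. Reproduce the plan's own power.** Inputs: n = 52, null ORR 60%, success if the exact 90% CI lies above 60% (1-sided alpha 0.05; Protocol 10.1, SAP 3.2). The Clopper-Pearson lower limit is L(x, n) = the 5% quantile of Beta(x, n − x + 1). The smallest x with L > 0.60 at n = 52 is 38.

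- Exact alpha = P(X ≥ 38 | 52, 0.60) = 0.0350.
- Power at 80% = P(X ≥ 38 | 52, 0.80) = 0.9183 (plan: 91.8%).
- Power at 75% = P(X ≥ 38 | 52, 0.75) = 0.6916 (plan: 69.2%).

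The other six rows of the power table reproduce as well, so no stated power figure is wrong.

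**3. Possible size.** Outside the set: 54 − 52 = 2, and 2/54 = 3.7%. Assumption: 0, 1 or 2 of them took pomalidomide or dexamethasone and did not respond. The any-treatment denominator is then 52, 53 or 54.

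| n | ORR at 38 responders | Lower 90% limit | Objective met? | Threshold | ORR at 42 responders |
|---|---|---|---|---|---|
| 52 | 73.1% | 61.2% | yes | 38 | 80.8% |
| 53 | 71.7% | 59.8% | no | 39 | 79.2% |
| 54 | 70.4% | 58.5% | no | 39 | 77.8% |

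At 38 responders the ORR falls by 73.1 − 71.7 = 1.4 points, or 73.1 − 70.4 = 2.7 points. At 42 responders, near the planning rate of 80%, it falls by 1.5 or 3.0 points (from unrounded values).

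**4. How often would the conclusion change?** The threshold moves from 38 to 39 whether one or two non-responders are added, so only exactly 38 responders matters. With the 52 infused subjects responding at the design rate:

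- True ORR 80%: P(X = 38) = 0.9183 − 0.8581 = 0.060.
- True ORR 75%: P(X = 38) = 0.6916 − 0.5738 = 0.118.

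These are conditional on at least one dosed non-responder among the two.

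**5. Key secondary endpoint.** The smallest count whose lower limit exceeds 3% is 5 at n = 52, 53 and 54 (5/52: 3.87%; 5/54: 3.72%; 4/52: 2.67%). The threshold does not move.

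**The case against.** **The condition is open and consistent.** It appears in the set definition, the ORR and MRD[-]CR denominators and the n = 52 power rows. Enrollment closed in late 2021 and the current SAP is dated September 2022, so changing the primary denominator of an open-label trial now carries its own risk. This stands, and it is why the primary test should stay on the 52.

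**There may be nobody affected.** Enrollment is the investigator's eligibility decision and precedes treatment. The SAP version that introduced the 54 and 52 figures also added the enrolled-but-not-dosed line. Two wholly undosed subjects would fit those facts. This stands as a limit on size, but the documents do not settle it.

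**Safety data are not lost.** Protocol 9.2.4.1 collects adverse events from consent to 30 days after the last dose of the three drugs, serious events go to the sponsor within 24 hours, and an internal team reviews safety data. This stands: the defect is in the planned tables.

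Two stronger readings are tempting, and the documents support neither:

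- A reader might infer from Protocol 7.4.1.1 that a missed first infusion is never made up, leaving a week or more on the other two drugs. That rule concerns within-cycle doses. A delayed day 1 shifts the cycle, and dosing may resume at the next planned date, so a later infusion brings the subject into the set. The gap needs a subject who is never infused at all.
- A reader might infer that the exclusion can only raise the ORR. That holds for non-responders. A subject on pomalidomide without carfilzomib is still on protocol treatment (7.4.1.1), and Protocol 3.2.3.1 cites a 31% ORR for pomalidomide with dexamethasone. Excluding a never-infused responder would lower the ORR.

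**Conclusion.** The mismatch is real and should be corrected, mainly for the safety tables. A subject dosed only with pomalidomide or dexamethasone has treatment-emergent events by the SAP's definition and appears in no table, denominator, sensitivity set or fitting disposition line.

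The number affected is 0 to 2 of 54, and unknown. The effect on efficacy is small and confined to the boundary: it rests on at least one of the two having been dosed without responding, and on exactly 38 responders among the 52. The MRD[-]CR decision rule is unaffected. This does not show that any event has gone unreported, or that the primary result is biased.

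**What to change.** 1. In Protocol 10.2.1 and SAP 6.2, define the population for safety analyses as enrolled subjects with at least 1 dose of any study treatment (carfilzomib, pomalidomide or dexamethasone), matching the treatment-emergent definition.
2. Keep a separately named carfilzomib-treated set (n = 52) for the primary ORR and key secondary MRD[-]CR tests, so the decision rules and power rows stand.
3. Add ORR in the any-treatment set and in all 54 enrolled to the sensitivity analyses in SAP Table 9-1.
4. In SAP 9.2, add a line for subjects dosed with pomalidomide or dexamethasone only, and state that not dosed means none of the three drugs.

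Cost: wording, at most two more subjects in the safety tables, and two sensitivity rows. If neither subject was dosed, the safety tables and the any-treatment ORR are the same as on the 52, and only the all-enrolled row differs.
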